#### **Reference Measurements**

The following parameters will be measured and recorded using values closest in time to 8:00 A.M. on the days specified in the Time-Events schedule (Appendix F). The following conditions will be ensured prior to measurements: no endobronchial suctioning for 10 minutes; no invasive procedures or ventilator changes for 30 minutes. All vascular pressures will be zero-referenced to the mid-axillary line with the patient supine.

- 1) If receiving assisted ventilation record daily up to day 7:
  - a) Tidal volume, FiO2, PEEP, inspiratory plateau pressure, and mean airway pressures
  - b) Pressure during inspiration if on a pressure targeted mode (PSV, PCV, etc).
  - c) Arterial PaO2, PaCO2, pH and SpO2
- 2) CK, AST, ALT as in schedule of events (Appendix F)
- 3) Fluid intake and output
- 4) Vital signs: Heart rate, systolic and diastolic blood pressure, body temperature, CVP
- 5) Modified Brussels Score data days 0-14:
  - a) Vasopressor use (Y/N), worst systolic BP, creatinine, bilirubin, and platelet count for the day. The date and value of the highest creatinine between days 15-28
- 6) CAM-ICU delirium screening assessment and RASS or RIKER sedation score through ICU discharge or study day 28 at select hospitals
- 7) Presence of myopathy
  - 8) Frontal Chest Radiograph Lung Injury Score
- 9) Occurrences of VTE, myocardial infarction, bowel ischemia, ischemic stroke and arrhythmias requiring treatment
- 10) Methylprednisolone equivalents greater than 20 mg
- 11) Daptomycin administration
- 12) Concomitant medications: niacin, fenofibrate, cyclosporine, gemfibrozil, lopinavir, ritonavir, or oral contraceptives. (Yes/No each day). The type and dose of statins prescribed as part of usual care if the study drug is withdrawn by the treating physician during the treatment period or prescribed after the treatment period will be recorded.
- a) Study drug/placebo will be stopped should one of these medications be started.
   13) Blood and urine for cytokines, mediators, and markers of inflammation. Plasma obtained from two, 10 ml EDTA anti-coagulated blood samples will be divided immediately after centrifugation into 4 equal 2 ml aliquots and frozen at -70°C. Urine obtained from the patients will be collected in an 8 ml sample tube and divided into 4 equal aliquots in specified tubes and frozen at -70°C. Specimens will be collected on days 3 and 6.
- 14) Plasma CRP levels on days 6 and 14
  - a) CRP will be followed as statins have been shown to acutely reduce CRP in septic and non-septic patients and could serve also serves as a biomarker of effect.
- 15) Blood for statin peak and trough levels (day 6, plus or minus one day)

Samples will be sent to a central repository to be stored (as described below). Samples will be identified by central repository accession numbers during shipment and storage in the central repository. In the future, when studies using the samples are approved, and are requested during the NHLBI *proprietary period*, the clinical coordinating center (CCC) will instruct the repository

to prepare the appropriate samples for shipment. The key relating the ARDSNet subject study ID number to the new specimen accession number will be kept at the CCC in a restricted access electronic file. The CCC will not record or store unique patient identifiers (such as initials, date of birth, hospital record numbers, addresses, phone numbers, etc.) in the database. All data released by the CCC for studies will be linked to the specimen but will be de-identified. The link (key) between the de-identified database and the patient will be removed two years after the primary publication. Urine and plasma collected for this trial will be frozen and stored at a bio-repository for future research.

#### 6.4 Assessments after Hospitalization

The following data, as well as vital status, will be collected at 6 and 12 months after ICU discharge (for the first 310 subjects enrolled into the SAILS trial **and then at select hospitals after the first 310 subjects enrolled**). We will collect this data through telephone interviews with patients. In addition, we will verify duration of survival for patients lost to follow-up or noted to have died using the Centers for Disease Control and Prevention's National Death Index (National Death Index, 2000). We will use each patient's social security number (SSN) for an exact NDI match. We will collect contact information for the patient and alternative contact information on up to 3 individuals. This information and the SSN will be collected on paper at the time of consent, and forward via secure fax to the CCC. Contact information and SSN will be maintained on paper and will not appear in the CCC database.

The following instruments will be used in data collection. This battery of instruments will be pilot tested to guarantee feasibility. The text explains the alternative tests available pending the results of the pilot testing.

- 1. Health-related Quality of Life:
  - *a.* SF-36 (consider the SF-12 if the length is too long in pilot testing). *Estimated administration time: 6 minutes.*
  - b. Euro-QOL (EQ-5d): Estimated administration time 2 minutes.
- 2. Psychological Outcomes:
  - a. Depression and Anxiety: Hospital Anxiety and Depression Scale (14 questions) *Estimated administration time: 5 minutes*
  - b. Post-Traumatic Stress Disorder (PTSD): Impact of Events Scale—Revised (22 questions); *Estimated administration time: 3 minutes*.
- 3. Neurocognitive Outcomes:
  - a. Neurobehavioral Cognitive Status Examination,
  - b. Wechsler Memory Scale
  - c. Wechsler Adult Intelligence Scale
  - d. Controlled Oral Association Test
- 4. Physical Activity Outcomes:

- *a.* Overall: Functional Performance Inventory-Short Form (32 questions) (alternative: deleting this instrument (due to overlap with the Physical Function Domain of SF-36) or use the Katz ADL (6 questions) & the Lawton IADL, (8 questions), if length is too long in pilot testing) *Estimated administration time: 5 minutes*
- b. Work disability: Return to Work Custom-made Questionnaire (12 questions—will reduce number of questions if length is too long in pilot testing); *Estimated administration time: 2 minutes*.
- 5. Health care utilization: Custom-made instrument developed based on University of Toronto ARDS Outcome Study instrument provided by [name] (27 questions), will reduce number of questions if this instrument is too lengthy in pilot testing; *Estimate administration time: 8 minutes*

### 6.5. Endpoint Determinations

- 1. Vital status at 60 days until discharged home on unassisted breathing.
- 2. Brussels Organ dysfunction failures at days 0-14
- 3. Time of initiation of unassisted breathing (assuming a patient achieves 48 consecutive hours of unassisted breathing)
- 4. Need for re-instituting assisted or mechanical ventilation after achieving 48 consecutive hours of unassisted breathing
- 5. Need for, timing, and duration of dialysis
- 6. Status 48 hours after initiation of unassisted breathing
- 7. ICU length of stay in calendar days including ICU days after readmission to ICU.
- 8. Hospital length of stay in calendar days and discharge disposition (home, other facility, with or without assisted ventilation)
- 9. For rosuvastatin toxicity:
  - a. CK > > 10 times ULN
  - b. ALT > 8 times ULN
  - c. AST > 8 times ULN

# 7. Statistical Considerations

# 7.1. Statistical Methods

At interim analyses hospital mortality to day 60 will be estimated using the Kaplan Meier estimate with patients who are discharged home considered as censored at day 61. At the final analyses where 60 day mortality will be known for everyone the binomial estimate will be used. The analysis will be stratified by co-enrolled treatment assignments if applicable. VFDs, ICU free days and hospital free days will be analyzed by analysis of variance, with treatment (active, placebo) and co-enrolled assignment if applicable. A secondary analysis will correct for the covariates for mortality developed from previous ARDS Network trials.

#### 7.2. Early Stopping and Monitoring

Given the interest in statin therapy the monitoring boundaries were designed to have a relatively low probability of stopping for futility before 750 patients in order to avoid a trial which is equivocal as to whether or not statins are effective.

The maximum sample size will be 1000 patients. The study will be monitored using a flexible group sequential design that includes potential stops for both efficacy and futility. Efficacy stopping will be based on mortality alone while futility stopping will be based on both mortality and VFDs. The reported confidence intervals on the treatment difference will be adjusted for the group sequential design using the method of Jennison and Turnbull for interim analyses.

The alpha and beta spending boundaries have been developed using EAST (Cytel Inc). The table below gives the boundaries for the planned interim analyses occurring at 100, 250,500 and 750 patients with a final analysis at 1000 patients. For analyses at these times these boundaries are extrapolated using cubic splines to have the same error spending functions.

When reviewing the table below, suppose that we are at the second interim analysis after 500 patients. The study would stop for efficacy if the difference in mortality between the active and the placebo arm was 11% in favor of the active arm. We would stop for futility if both the placebo arm had better mortality than the active arm (by a difference of 1.3%) and the placebo arm had more ventilator free days (by a difference in 0.33 days). In terms of p-values to stop for efficacy, the p-value for the mortality difference would need to be less than 0.001525 one sided. To stop for futility the p-value for both survival and ventilator free days would have to be greater than 0.6392 one sided.

	Efficacy Boundary		Futility Boundary		
Number of Patients	Difference in Mortality Active- Placebo	p-value one sided	Difference in Mortality Active-Placebo	Difference in VFD Active-Placebo	p-value one sided
100	-0.60	3.4E-14	.28	-7.33	0.9998
250	-0.26	1.84E-07	0.055	-1.44	0.8614
500	-0.11	0.001525	0.013	-0.33	0.6392
750	-0.069	0.009162	-0.013	0.33	0.3343
1000	-0.051	0.022001	-0.051	1.34	0.0220

**Table 1: Efficacy and Futility Stopping Boundaries** 

With the sample size given the study has a 92% probability of rejecting the null hypothesis effect on mortality if the true difference in mortality is 9% (From 27% to 18%). The probability of rejecting the null hypothesis effect on VFDs is 92% assuming that the difference is 2.25 and the standard deviation of VFDs is 10.5.

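### The 92% power for ventilator-free days in section 7.2 holds at 1000 patients; under the written stopping rule and the planned mortality effect it is about 87–90%

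*Protocol*

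**What the plan says.** Under Table 1, section 7.2 of the protocol says that the given sample size yields 92% power for mortality at 27% versus 18%. The next sentence reads "The probability of rejecting the null hypothesis effect on VFDs is 92% assuming that the difference is 2.25". Its assumed SD is 10.5 days. It mentions neither early stopping nor an assumed mortality effect.

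The monitoring rule is set out earlier in the same section: "Efficacy stopping will be based on mortality alone while futility stopping will be based on both mortality and VFDs". It names "planned interim analyses occurring at 100, 250,500 and 750 patients with a final analysis at 1000 patients". Table 1 gives mortality both an efficacy and a futility boundary, and gives VFDs a futility boundary only.

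Section 3.2 gives VFDs to day 28 their own heading, ahead of the other secondary endpoints. Section 1.9 justifies mortality and VFDs together as the primary and secondary outcomes.

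**The concern.** The two 92% figures read as matching properties of one design. The mortality figure is one. The VFD figure uses the full 1000 patients, yet the design is built to finish early when mortality improves as hoped. In that scenario VFDs are usually compared on 500 or 750 patients.

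What is at stake is how a VFD result is read after an early mortality stop. The plan implies about an 8% chance of missing a true 2.25-day effect. Under its own planning scenario the chance is about 10–13%. A non-significant VFD result would then be judged against a power that the trial did not have.

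**Working it through.** **Inputs from section 7.2 and Table 1**
- Maximum 1000 patients, taken as 500 per arm (1:1 allocation is assumed).
- VFD difference 2.25 days, SD 10.5. Mortality 27% versus 18%.
- Efficacy p-values (one-sided, mortality) at 100/250/500/750/1000: 3.4E-14, 1.84E-07, 0.001525, 0.009162, 0.022001.
- Futility p-values, to be exceeded by both endpoints: 0.9998, 0.8614, 0.6392, 0.3343, 0.0220.

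**Input not in the protocol:** the correlation between the mortality and VFD test statistics. It should be clearly positive, because section 3.2 scores a death before day 28 as zero VFDs. Table 3 (no effect), read as futility stops as its caption indicates, prints 6%, 19% and 32% at 250, 500 and 750. Simulated futility stops are 6.0/17.7/31.1% at correlation 0.6 and 7.1/18.6/30.9% at 0.7, but only 3.6/14.8% at the first two of these looks at 0.3. I therefore use 0.60–0.75 and show 0.3–0.8 as the wider range.

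**Step 1: reproduce the stated figure.** Standardised effect = 2.25 / (10.5 × √(2/500)) = 2.25 / 0.664 = 3.39. Power at one-sided 0.025 = Φ(3.39 − 1.96) = 92.3%. At one-sided 0.022 it is Φ(3.39 − 2.01) = 91.5%. So 92% is correct for 1000 patients.

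**Step 2: VFD power at the earlier looks (one-sided 0.025).**
- 500 patients: 3.39 × √0.50 = 2.40; Φ(2.40 − 1.96) = 66.9%.
- 750 patients: 3.39 × √0.75 = 2.93; Φ(2.93 − 1.96) = 83.5%.

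**Step 3: where the trial stops under 27% versus 18%.** Simulating the five looks with efficacy on mortality alone and futility on both endpoints:
- stops at 250: about 0.04%
- stops at 500: about 29%
- stops at 750: about 44%
- reaches 1000: about 27%

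Mean size is about 745 and mortality power about 92%. Futility stops before the final look are about 0.1–0.3%, so they do not affect the result. Table 2 prints 28% and 44% at 500 and 750, which agrees.

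**Step 4: VFD power at the stopping look.** If the endpoints were uncorrelated, the answer would be the weighted average: 0.29 × 66.9 + 0.44 × 83.5 + 0.27 × 92.3 = 19.4 + 36.7 + 24.9 = 81.0%. Positive correlation raises this, because trials that stop early on mortality also tend to have favourable VFD data. By simulation, VFDs tested once at the stopping look at one-sided 0.025:

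| Correlation | VFD power |
|---|---|
| 0.3 | 84.2% |
| 0.5 | 86.4% |
| 0.6 | 87.6% |
| 0.7 | 88.9% |
| 0.75 | 89.4% |
| 0.8 | 90.3% |

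A patient-level simulation scoring deaths as zero VFDs (correlations 0.54–0.73) gave 87–91%, against 92–93% for the same data taken to 1000 patients.

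**Step 5: sensitivity.**
- *Overrun.* With 60 extra patients analysed past an early look (an assumed number), power is 88.8–90.2% for correlation 0.60–0.75.
- *No mortality effect.* Almost no trial stops early for efficacy, and VFD power stays at about 92%. With half the planned effect it is 90–92%.

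**Side check on Table 2.** Its rows add to 12 + 28 + 44 + 19 = 103%, against a printed total of 91.68%. Without the 12% at 250 they add to 91%. That 12% cannot be reproduced from the Table 1 boundary at 250 (about 0.04%), so the figures above use the boundaries and not that row.

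**The case against.** The strongest reply is that nothing was miscalculated. The sentence refers to the given sample size, conditions only on the VFD difference and SD, and reproduces. It does not claim to average over mortality-driven stops. That is right as to the arithmetic. But the sentence sits in the monitoring section, beside a mortality figure that does survive the rule. Table 1 also pairs mortality and VFD differences (−0.051 with 1.34), so the joint alternative is the natural planning scenario.

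It is also fair that the source of the 92% is not documented. A sequential trial with the same boundaries, stopped on VFDs, would give 91.9%. That is not the written rule either.

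The size of the loss depends on an assumed correlation. At 0.8 the figure is within 2 points of 92%, and overrun narrows the gap further. VFDs are secondary, and the loss arises mainly once a mortality benefit has been shown. All of this stands and limits the weight of the point.

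A reader might go further and infer that VFD power is only 72–75%, because section 7.2 says: "The reported confidence intervals on the treatment difference will be adjusted for the group sequential design using the method of Jennison and Turnbull". That figure arises only if VFDs must meet the mortality efficacy p-value of the stopping look. The protocol does not require this: Table 1 assigns VFDs no efficacy boundary, the adjustment sentence does not name VFDs, and section 7.1 analyses them by analysis of variance with no sequential level. It should not be used as a replacement figure.

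**Conclusion.** The point holds in a limited form. The 92% is the VFD power with 1000 patients, or without mortality-driven stops. With mortality falling from 27% to 18%, the written rule delivers about 87–90% at nominal one-sided 0.025 for correlation 0.60–0.75, and 84–90% for 0.3–0.8. Analysing overrun patients recovers about 1 point. These figures rest on 1:1 allocation, the Table 1 p-values, a single VFD test at the stopping look, and a correlation that the protocol does not state.

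The documents do not support reading this as a fault in the stopping rule or as an underpowered trial. The mortality power is sound, and the VFD shortfall is a few points on a secondary endpoint. The statement still needs correcting, because the design does not deliver the stated power in the scenario it was planned for.

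**What to change.** Reword the VFD sentence in section 7.2 so that 92% is the power if the trial reaches 1000 patients. Beside it, give the VFD power under the sequential rule for the joint alternative (27% to 18%, 2.25 days, SD 10.5). State the one-sided level, the correlation, and whether patients enrolled past a look are counted.

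Take that figure from a rerun of the simulation, not from the existing Table 2 output, whose rows do not agree with its own total. Correct Table 2 at the same time, including the text that adds its 12% and 28%.

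The cost is one sentence and a simulation rerun. The stated VFD power becomes a few points less favourable. Boundaries, sample size and procedures stay as they are.

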# **Simulation of Stopping Bound Properties**

Table 2 gives the results of 10,000 computer simulated clinical trials using the efficacy and futility boundaries described above, assuming that rosuvastatin truly reduces mortality by 9%

(from 27% to 18%). For example, if rosuvastatin is effect then we would have a 40% chance (12% + 28%) of stopping on or before the 500 patient look.

Sample size at scheduled interim analysis	Percent of simulations that stop the trial for efficacy
100	
250	12%
500	28%
750	44%
1000	19%
Total %	91.68%

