#### Table 2: Simulations of SAILS under the assumption rosuvastatin is effective

Table 3 gives the results of 10,000 computer simulated clinical trials assuming that rosuvastatin has no effect on mortality. For example, if rosuvastatin has no effect on either VFD or mortality then we would have a 25% chance of stopping on or before the 500 patient look.

 

 Table 3: Simulations of SAILS under the assumption rosuvastatin is not effective (note: futility includes both VFD and Mortality)

Sample size at scheduled interim analysis	Percent of simulations that stop the trial for efficacy
100	0.0%
250	6%
500	19%
750	32%
1000	38%
Total %	96%

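### Table 2 overstates the chance of an early efficacy stop: 12% at 250 patients and 40% by 500, where the protocol's own boundaries give well under 0.1% and about 29%

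*Protocol*

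**What the plan says.** Protocol section 7.2 sets the design: "The maximum sample size will be 1000 patients", with "planned interim analyses occurring at 100, 250,500 and 750 patients with a final analysis at 1000 patients". It also says that "Efficacy stopping will be based on mortality alone while futility stopping will be based on both mortality and VFDs".

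Table 1 gives the efficacy boundary at each look. At 250 patients it is a mortality difference of -0.26, one-sided p 1.84E-07. At 500 it is -0.11, and "the p-value for the mortality difference would need to be less than 0.001525 one sided". The one-sided p-values at 750 and 1000 are 0.009162 and 0.022001.

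Below Table 1 the protocol states its power: "With the sample size given the study has a 92% probability of rejecting the null hypothesis effect on mortality if the true difference in mortality" matches the assumed fall of 9 points, from 27% to 18%.

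Table 2 is introduced as 10,000 simulated trials run with those boundaries, "assuming that rosuvastatin truly reduces mortality by 9" points. Its column, "Percent of simulations that stop the trial for efficacy", reads 12% at 250, 28% at 500, 44% at 750 and 19% at 1000, with a total of 91.68%. The text adds the first two: "we would have a 40% chance (12% + 28%) of stopping on or before the 500 patient look".

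Table 3 covers the case of no effect. It carries the same column heading, with rows 0.0%, 6%, 19%, 32% and 38% and a total of 96%. Its caption notes that futility includes both VFDs and mortality.

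**The concern.** A trial can stop for efficacy at only one look, so the rows of Table 2 are mutually exclusive and must add to the total. They add to 103%, which is not a possible probability.

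The 250 row also conflicts with Table 1. A boundary beyond five standard errors cannot be crossed in one trial in eight when the assumed effect is worth less than two standard errors at that look.

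These figures are the stated operating characteristics of the stopping rules that the DSMB applies. A reader who takes them at face value expects an effective drug to stop the trial at 250 patients about 12% of the time, and by 500 patients 40% of the time. That reader would underestimate the expected trial size and read too much into the absence of an early stop.

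**Working it through.** **Inputs.** Mortality 27% (placebo) and 18% (active), looks, maximum sample size and boundaries are from section 7.2. The allocation ratio is not stated in section 4.6; 1:1 is assumed, giving 125 per arm at 250 and 500 per arm at 1000.

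**1. Reproduce the stated power.** A fixed-sample comparison of 27% with 18%, 500 per arm, has power 0.920 at one-sided 0.022001 and 0.927 at two-sided 0.05. The protocol's 92% reproduces.

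**2. Add the rows of Table 2.** 12 + 28 + 44 + 19 = 103, which exceeds 91.68 by 11.32 points. Rounding four rows to whole percentages explains at most 4 × 0.5 = 2 points. Without the 250 row, 28 + 44 + 19 = 91, in line with 91.68. Even with those three rows at their lowest unrounded values (27.5 + 43.5 + 18.5 = 89.5), the total leaves at most 91.68 − 89.5 = 2.18% for the 250 row.

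**3. Chance of crossing at 250.**
- Boundary: one-sided p 1.84E-07 is z = 5.085.
- Standard error of the difference: √[(0.27×0.73 + 0.18×0.82)/125] = √(0.3447/125) = 0.0525.
- Expected z: 0.09/0.0525 = 1.714.
- Chance of crossing: Φ(1.714 − 5.085) = Φ(−3.371) = 0.037%.
- With the difference boundary instead: Φ((0.09 − 0.26)/0.0525) = 0.060%.
- Exact binomial, 125 per arm: 0.022% (pooled z), 0.058% (unpooled z), 0.059% (difference of at least 0.26).

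In 10,000 simulated trials this is about 2 to 6 stops. A 12% rate would be 1,200.

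**4. What 12% would require.** The boundary would have to be at z = 1.714 + 1.175 = 2.889, a one-sided p of about 0.0019 or a difference of 2.889 × 0.0525 = 0.152. Table 1 has 1.84E-07 and 0.26.

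**5. Chance of crossing at 500.** The standard error is √(0.3447/250) = 0.0371 and the expected z is 2.424. Φ(2.424 − 2.963) = Φ(−0.539) = 29.5%.

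**6. All five looks together**, 400,000 simulated trials per setting:

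| Look | Table 2 | p boundary, pooled z | p boundary, unpooled z | Difference boundary |
|---|---|---|---|---|
| 250 | 12% | 0.02% | 0.06% | 0.06% |
| 500 | 28% | 29.1% | 29.7% | 29.4% |
| 750 | 44% | 43.9% | 43.3% | 47.4% |
| 1000 | 19% | 19.3% | 19.4% | 16.6% |
| Total | 91.68% | 92.4% | 92.5% | 93.5% |

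With the pooled p-value boundaries the later rows and the total agree with Table 2 to about a point. Only the 250 row fails.

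**7. Variants.** Futility was applied on mortality and VFDs jointly (assumed correlation 0, 0.5 or 0.8) and on mortality alone. No variant brings the 250 row above 0.1%. Counting futility stops under the alternative adds less than 0.6 points by 500, so they do not account for 40% either.

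**8. Table 3.** With no effect, the p-value boundaries give efficacy stops of about 0, 0, 0.15, 0.8 and 1.5%, in total 2.5%. Applying the joint mortality-and-VFD futility rule at every look gives 95.4% to 96.3% for assumed correlations of 0 to 0.8. The printed 96% is therefore a futility figure under an efficacy heading.

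**The case against.** The strongest reply is that nothing operative is wrong. The DSMB acts on Table 1, not on Table 2, and Table 1 prints the 26-point difference and the 1.84E-07 just above the faulty row. The power, the printed total and the other rows reproduce. This stands, and it limits the weight of the point: enrolment, error control and the final analysis do not depend on the 12%.

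A second reply is that 12% is a misplaced decimal. With 0.12% the rows sum to 0.12 + 28 + 44 + 19 = 91.12, close to 91.68. That is possible but cannot be confirmed without the simulation output. It would not clear the text, which repeats the 12% and adds it into the 40%.

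A reader might infer from Table 3 that the design has a 96% false-positive rate. The documents do not support that. The caption refers to futility, the lead-in describes no effect on either endpoint, and the joint futility rule reproduces the 96%. The heading has simply been carried over from Table 2. Relabelling the column as failure to reject would also be inaccurate: non-rejection on mortality is about 97.5%, not 96%. The lack of a tabulated type I error is no fault either, since a protocol may leave fuller operating characteristics to the SAP.

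**Conclusion.** Wrong as written, of moderate weight. The 12% at 250 patients is about 200 times too high (12/0.06) to 600 times too high (12/0.02). The 40% by 500 is about 10 points too high against a recomputed 29% to 30%. The printed rows sum to 103% against a total of 91.68%.

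The result assumes 1:1 allocation and complete outcomes at each look. Marked imbalance or incomplete 60-day follow-up would reduce the information at 250 and so lower the crossing chance further.

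A reader might conclude that the stopping boundaries or the sample size are unsound. That does not follow: the boundaries and the 92% power are consistent with each other and with the later rows of Table 2. What is wrong is the description of early stopping.

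**What to change.** Re-issue the 250 row of Table 2 from the simulation output. It should be well under 1%; recomputation gives about 0.02% to 0.06%. Replace the 40% and its sum with the matching cumulative figure, about 28% to 29%: the table's own 500 row plus a negligible 250 row gives 28%, and recomputation gives about 29%. Then check that the rows add to the stated total within rounding.

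As a minor correction, relabel the Table 3 column as stopping for futility on both mortality and VFDs.

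The cost is a text and table correction. No boundary, power statement, sample size or trial procedure changes. The stated chance of an early efficacy stop becomes less favourable.
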